## PROTOCOL SYNOPSIS

**Gilead Sciences, Inc.**  
**[name]**  
**[name]**

---

**Study Title:** A Phase 2, Randomized, Double-Blind, Placebo-Controlled Study Evaluating the Safety, Tolerability, and Efficacy of GS-0976 in Subjects with Nonalcoholic Steatohepatitis

---

**IND Number:** 124915  
**EudraCT Number:** Not Applicable  
**Clinical Trials.gov Identifier:** Not Available

---

**Study Centers Planned:** Approximately 50 centers in the United States

---

[figure not shown]
**Objectives:** The primary objective of this study is to evaluate the safety and tolerability of GS-0976 in subjects with nonalcoholic steatohepatitis (NASH) as assessed by magnetic resonance imaging-proton density fat fraction (MRI-PDFF) and magnetic resonance elastography (MRE) or a historical liver biopsy consistent with NASH and non-cirrhotic fibrosis. The exploratory objectives of this study are listed in Section 2.

---

**Study Design:** This is a Phase 2 randomized, double-blind, placebo-controlled study evaluating the safety, tolerability, and biological activity of GS-0976 in subjects with NASH as assessed by MRI-PDFF and MRE, or a historical liver biopsy consistent with NASH and non-cirrhotic fibrosis.

Participation in the study can last up to approximately 22 weeks, which includes a 6-week Screening period, a 12-week treatment period during which study drugs will be administered, and a 4-week follow-up period. The screening period may be extended under special circumstances with the explicit approval of the Medical Monitor.

Subjects meeting the study's entry criteria will be randomly assigned in a 2:2:1 ratio to 1 of 3 treatment groups as shown in the figure below:

Study drugs will be administered for a total of 12 weeks. Randomization will be stratified by the presence or absence of diabetes mellitus as determined by medical history, use of medication for indication of diabetes mellitus, or based on Screening lab values if previously undiagnosed (i.e., hemoglobin A1c  $\geq$  6.5% OR fasting plasma glucose  $\geq$  126 mg/dL).

Number of  
 Subjects  
 Planned:

Approximately 125 subjects

Target  
 Population:

Males and non-pregnant, non-lactating females between 18-75 years of age without cirrhosis and with NASH as assessed by MRI-PDFP and MRE or a historical liver biopsy consistent with NASH and non-cirrhotic fibrosis.

Duration of  
 Treatment:

Subjects will be treated for 12 weeks.

Diagnosis and  
 Main Eligibility  
 Criteria:

Key inclusion and exclusion criteria are as follows:

**Key Inclusion Criteria:**

- Meets the following conditions:
  - a) A clinical diagnosis of nonalcoholic fatty liver disease (NAFLD) with imaging or a liver biopsy documenting fatty liver within two years prior to Screening (if necessary, an ultrasound may be performed during Screening to confirm NAFLD), and
  - b) Screening MRI-PDFP with  $\geq$  8% steatosis, and
  - c) Screening MRE with liver stiffness  $\geq$  2.5 kPa.

Note: criterion a. must be met before evaluating criteria b. and c.

OR

- A historical liver biopsy within 12 months of Screening consistent with NASH (defined as the presence of steatosis, lobular inflammation, and hepatocellular ballooning) with fibrosis, but not cirrhosis, and
- No documented weight loss > 5% between the date of the liver biopsy and Screening.
- Platelet count  $\geq 100,000/\text{mm}^3$
- Creatinine Clearance ( $\text{CL}_{\text{cr}}$ ) as calculated by the Cockcroft-Gault equation  $\geq 60$  ml/min

**Key Exclusion Criteria:**

- Pregnant or lactating females;
- ALT > 5 x ULN;
- Other causes of liver disease including autoimmune, viral, and alcoholic liver disease;
- Cirrhosis of the liver as defined by any of the following:
  - a) Cirrhosis on historical liver biopsy (e.g. NASH CRN classification stage 4 or equivalent);
  - b) Evidence of cirrhosis on liver imaging (e.g. ultrasound, CT, or MRI) including a nodular liver surface, splenomegaly, or portal venous collaterals;
  - c) Prior history of decompensated liver disease, including ascites, hepatic encephalopathy or variceal bleeding;
  - d) Screening FibroSURE/FibroTest®  $\geq 0.75$ , unless a historical liver biopsy within 12 months of Screening does not reveal cirrhosis. In patients with Gilbert's syndrome or hemolysis, FibroSURE/FibroTest® will be calculated using direct bilirubin instead of total bilirubin.
- BMI < 18 kg/m^2;
- INR > 1.2, unless on anticoagulant therapy;
- Total bilirubin > 1 x ULN, except with diagnosis of Gilbert's syndrome;

Refer to Sections 4.2 and 4.3 for complete listing of inclusion and exclusion criteria.

Subjects with laboratory abnormalities outside of the above parameters may be approved for inclusion in the trial with approval from the Medical Monitor.

Study  
Procedures/  
Frequency:

After signing the informed consent form, subjects will complete a Screening visit which will include the following assessments: complete medical history, physical examination (PE), vital signs, laboratory assessments (blood chemistry, hematology, coagulation panel, hemoglobin A1c, and HIV-1, HBV, and HCV serology), serum pregnancy test (for females of child-bearing potential), urine drug test, standard 12-lead ECG, ultrasound (if necessary), review of adverse events, concomitant medications, and MRI-PDF and MRE examinations.

After the Screening period and a randomization visit at Baseline/Day 1, study visits will occur on Weeks 1, 4, 8, 12, and a Follow-Up visit 4 weeks after the last dose of study drugs. At minimum, vital signs, symptom driven PE, safety laboratory tests (blood chemistry, hematology, coagulation panel, and lipid profile), review of adverse events and concomitant medications will be done at every visit.

Eligible subjects will be randomized to one of 3 treatment groups. Prior to initial dosing, required Baseline/Day 1 assessments will be performed and will include symptom driven PE, vital signs (including waist circumference), laboratory assessments, pregnancy tests (for females of child-bearing potential), urine, blood, and stool collection for biomarker assessment, Quality of Life (QoL) questionnaires, standard 12-lead ECG, FibroScan® (if available), review of adverse events and concomitant medications.

CCI  
[REDACTED]

While on study, subjects will undergo the following procedures and laboratory assessments:

- MRE and MRI-PDF at Week 12
- FibroScan® at Baseline/Day 1 and Week 12 (if available)
- Single PK sampling at Weeks 1, 4, 8, and 12
- Blood collection for Biomarkers at Baseline/Day 1, and at Weeks 1, 4, and 12
- Urine collection for Biomarkers at Baseline/Day 1, and at Weeks 1, 4, and 12
- 12-lead ECGs at Baseline/Day 1 and Week 12
- Hematology, blood chemistry, fasting lipid profile, PT, PTT, and INR at Baseline/Day 1, and at Weeks 1, 4, 8, 12, and Follow-Up visit
- Hemoglobin A1c (HbA1c) at Baseline/Day 1 and Week 12
- Stool collection for Biomarkers at Baseline/Day 1 and Week 12

- Urine pregnancy test (females of childbearing potential only) at Baseline/Day 1, and at Weeks 4, 8, 12, and Follow-Up visit
- SF-36, WPAI, and CLDQ at Baseline/Day 1 and Week 12

Subjects will return for their final visit, the Follow-Up visit, 4 weeks after the last dose of study drugs. At this visit assessments include a symptom driven PE, vital signs, review of concomitant medications and AEs, and safety laboratory tests. A urine pregnancy test will be performed for females of child bearing potential only.

CCI

---

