#### 1.2.5.2. Study 0976-102: Multiple Ascending Dose (MAD) Study

The multiple ascending dose (MAD) study (Protocol Number 0976-102) was a randomized, double-blind, placebo-controlled, clinical study conducted in healthy adult subjects at one study center in the United States. Five (5) cohorts of 8 subjects (6 active and 2 placebo) were evaluated at the following GS-0976 doses: 50 mg BID (100 mg daily) or placebo, 100 mg QD (100 mg daily) or placebo, 100 mg BID (200 mg daily) or placebo, 200 mg QD (200 mg daily) or placebo, or 150 mg QD (150 mg daily) or placebo. In each cohort, subjects received multiple

oral doses of GS-0976 or placebo BID (every 12 hours) or once daily (QD) for 9 consecutive days (Days 1 through 9), with a single oral dose of GS-0976 or placebo on the morning of Day 10. Doses were administered approximately 30 minutes after meals. Preliminary safety and PK data are available for the first 4 dose groups.

Each of the first 4 dose groups was fully enrolled and, overall, 24 subjects received GS-0976 and 8 subjects received placebo. The majority of these 32 subjects who received GS-0976 (19/24, 79%) and placebo (4/8, 50%) had at least 1 treatment-related AE as assessed by the principal investigator. The incidence of treatment-related AEs appeared to increase with higher doses and BID dosing of GS-0976: 50% of subjects at 50 mg BID, 62.5% at 100 mg QD, 75% at 200 mg QD, and 100% at 100 mg BID. One subject in the 200 mg QD cohort discontinued due to an AE on study Day 7 for Grade 4 elevated triglycerides (TG). No deaths or SAEs were reported.

The most frequently reported TEAEs were gastrointestinal disorders and involved nausea (33% of all subjects who received GS-0976 vs. 0% of all subjects who received placebo), abdominal distension (25% GS-0976 vs. 13% placebo), constipation (21% GS-0976 vs. 13% placebo), diarrhea (21% GS-0976 vs. 0% placebo), and vomiting (13% GS-0976 vs. 0% placebo). In addition, TEAEs of increased blood triglycerides were reported (25% GS-0976 vs. 0% placebo) and involved Grade 3 events in 5 subjects (3 subjects in the 100 mg BID cohort and 2 subjects in the 50 mg BID cohort), and a Grade 4 event in 1 subject in the 200 mg QD cohort (discontinued treatment).

There were no clinically important treatment-related or dose-related trends in vital signs, ECG, or physical examination assessments in this study.

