- 16) Unstable cardiovascular disease as defined by any of the following:
  - a) Unstable angina within 6 months prior to Screening
  - b) Myocardial infarction, coronary artery bypass graft surgery or coronary angioplasty within 6 months prior to Screening
  - c) Transient ischemic attack or cerebrovascular accident within 6 months prior to Screening
  - d) Obstructive valvular heart disease or hypertrophic cardiomyopathy
  - e) Congestive heart failure;
- 17) Use of prohibited concomitant medications as described in Section 5.4
- 18) History of a malignancy within 5 years prior to Screening with the following exceptions:
  - a) Adequately treated carcinoma in situ of the cervix
  - b) Adequately treated basal or squamous cell cancer or other localized non-melanoma skin cancer;
- 19) Any laboratory abnormality or condition that, in the investigator's opinion, could adversely affect the safety of the subject or impair the assessment of study results;
- 20) Participation in another investigational study of a drug or device within 28 days prior or within 5 half-lives of the prior investigational agent (whichever is longer) prior to Screening;
- 21) Concurrent participation in another therapeutic clinical study;

- 22) Known hypersensitivity to GS-0976, the metabolites, or formulation excipient;
- 23) Presence of any condition that could, in the opinion of the investigator, compromise the subject's ability to participate in the study, such as history of substance abuse or a psychiatric (including any subjects with a psychiatric hospital admission or emergency room visit in the 2 years prior to Screening) or medical condition;
- 24) Unavailable for follow-up assessment or concern for subject's compliance with the protocol procedures;
- 25) Contraindications or inability to complete MRI scanning (e.g. presence of permanent pacemakers, implanted cardiac devices, weight restrictions, etc.).

Subjects with laboratory abnormalities outside of the above parameters may be approved for inclusion in the trial with approval from the Medical Monitor.

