### **6.2. Pretreatment Assessments**

#### **6.2.1. Screening Visit**

Subjects will be screened within 6 weeks prior to randomization to determine eligibility for participation in the study. The Screening period may be extended under special circumstances with the explicit approval of the Gilead Medical Monitor.

Subjects who previously failed screening in GS-US-426-3989 can be re-screened in the following situations:

- Previously screen failed due to a low MRE or MRI-PDFF measurement, but have an MRE  $\geq 2.5$  kPa and MRI-PDFF  $\geq 8\%$  within 6 months of prior Screening/Re-screening.
- Previously screen failed due to a low MRE or MRI-PDFF measurement and have a historical liver biopsy within 12 months of Screening/Re-screening that is consistent with NASH (defined as the presence of steatosis, hepatocellular ballooning, and lobular inflammation) with fibrosis, but not cirrhosis.
- Previously screen failed due to a FibroSURE/FibroTest®  $\geq 0.75$  in whom Gilbert's syndrome or hemolysis is present; a repeat FibroSURE/FibroTest® calculated using direct bilirubin instead of total bilirubin will be used to determine eligibility.

- Previously screen failed due to a FibroSURE/FibroTest®  $\geq 0.75$  and with a historical liver biopsy within 12 months of Screening that does not reveal cirrhosis; FibroSure/Fibrotest score will not be used to determine eligibility.

If MRE and MRI-PDFF were performed within 6 months of re-screening, MRE and MRI-PDFF does not need to be repeated. If prior imaging was performed greater than 6 months prior to re-screening, MRE and MRI-PDFF must be repeated. A historical MRE and MRI-PDFF within 6 months of screening in another Gilead study (i.e. GS-US-384-3914, GS-US-402-1852) may be used to determine eligibility into this study. All other screening procedures must be repeated and meet eligibility criteria.

Screening labs may be repeated within the Screening period, prior to administration of study drugs to rule out laboratory error, if any. This will be done at the discretion of the investigator.

Subjects should be instructed to fast (no food or drink, except water), starting from midnight (00:00) or earlier, as appropriate, on the evening prior to the Screening visit to ensure an approximate 8-hour fast prior to the fasted blood sample collection the next morning.

The following will be performed and documented at Screening:

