### 6.3. Baseline/Day 1 Randomization and Assessments

Subjects returning to the clinic for randomization at Baseline/Day 1 should be instructed to fast (no food or drink, except water), starting from midnight (00:00) or earlier, as appropriate, on the evening prior to the Baseline/Day 1 visit to ensure an approximate 8-hour fast prior to the blood sample collection under fasting conditions the next morning.

After review of inclusion and exclusion criteria to confirm continued eligibility, subjects will be randomized to study drug assignment and receive their Subject Identification Number via the IWRS prior to their first dose of study drugs.

Randomization will be stratified by the presence or absence of diabetes mellitus as determined by medical history, use of medication for indication of diabetes mellitus, or based on Screening lab values if previously undiagnosed (ie, hemoglobin A1c  $\geq 6.5\%$  OR fasting plasma glucose  $\geq 126$  mg/dL).

The following will be performed and documented at the Baseline/Day 1 visit prior to dosing:

- QoL Questionnaires (SF-36, WPAI, and CLDQ)

Note: It is recommended that QoL questionnaires be completed prior to any study procedures being performed and prior to the subject seeing a health care provider.

- Symptom driven physical examination
- Record vital signs, waist circumference, and body weight
- Obtain blood samples for:
  - Chemistry
  - Hematology
  - Coagulation Panel
  - Lipid Profile
  - Hemoglobin A1c
  - Biomarkers
  - CCI
- Conduct standard 12-Lead ECG
- Perform FibroScan® (if available)
- Collect urine samples for:
  - Urine pregnancy test for females of child bearing potential only
  - Biomarkers
- Collect stool sample for Biomarkers (see Study Reference Binder for instructions)
- Dispense study drugs, and provide subject with instruction on appropriate dosing and administration; subject will take the Baseline/Day 1 dose of study drugs on-site
- Record all concomitant medications that the subject has taken since the previous visit
- Record any serious adverse events and all adverse events occurring since the Screening visit

Subjects will return to the investigative site at Week 1 ( $\pm 3$  days) for a mandatory safety visit. Then, starting at the Week 4 visit, subjects will have visits every 4 weeks up to the Week 12 visit.

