#### Additional Tests:

Lipid Profile, Hemoglobin A1c, HIV-1, HBV & HCV Serology (if HCV Ab positive, reflex to HCV RNA), urine drug screen (for amphetamines, cocaine, opiates), serum CCI and genomic sample collection.

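### Triglycerides are first measured at the visit of randomization and first dose, and nobody is required to see the result first; a Screening lipid profile would be a cheap, minor safety improvement

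*Protocol*

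**What the plan says.** The synopsis (Study Procedures/Frequency) gives the Screening blood work as "laboratory assessments (blood chemistry, hematology, coagulation panel, hemoglobin A1c, and HIV-1, HBV, and HCV serology", plus a pregnancy test. Protocol 6.2.1 lists the same panels. In Protocol Appendix 2 and SAP Appendix 1 the Lipid Profile row is empty under Screening and first marked at Baseline/Day 1.

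The Screening chemistry panel does not fill the gap. Section 6.8.1 lists its analytes without triglycerides or cholesterol, and puts lipids among the additional tests: "Lipid Profile, Hemoglobin A1c, HIV-1, HBV & HCV Serology".

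At Baseline/Day 1 (6.3), "After review of inclusion and exclusion criteria to confirm continued eligibility, subjects will be randomized to study drug assignment". The lipid sample is drawn before dosing, and at the same visit the "subject will take the Baseline/Day 1 dose of study drugs on-site". No section asks for the lipid result to be available before either step.

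No criterion in 4.2 or 4.3 names triglycerides. The one that could apply is exclusion 19: "Any laboratory abnormality or condition that, in the investigator's opinion, could adversely affect the safety of the subject".

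On the drug's history, section 1.2.5.2 says that reports of raised triglycerides "involved Grade 3 events in 5 subjects (3 subjects in the 100 mg BID cohort and 2 subjects in the 50 mg BID cohort", with "a Grade 4 event in 1 subject in the 200 mg QD cohort (discontinued treatment".

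**The concern.** Safety and tolerability is the primary objective, and section 1.4 treats triglyceride elevation as a risk to be mitigated. Section 1.1 links NASH to dyslipidemia, whereas the Phase 1 subjects were healthy or otherwise healthy. Yet of the four safety panels the synopsis names for study visits (chemistry, hematology, coagulation, lipids), only lipids is left out at Screening.

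Two things follow:

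- When the investigator applies exclusion 19, no scheduled triglyceride value need exist. A subject with a severe value that nobody knows about can be randomized and dosed.
- Protocol 8.3 replaces a missing laboratory baseline with the Screening result. For lipids there is no scheduled Screening result to use.

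**Working it through.** **Schedule check.** The synopsis does say that the lipid profile is done at every visit, but that sentence covers the visits after Screening. One Screening blood item in 6.2.1 is redacted. This does not matter, because the Lipid Profile row is legible in both schedules and blank at Screening.

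**The triglyceride signal** (Protocol 1.2.5.2; preliminary data, first four cohorts, 6 active subjects each, 8 placebo in all).

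| Cohort | Daily dose | Grade 3-4 |
|---|---|---|
| 50 mg BID | 100 mg | 2/6 |
| 100 mg BID | 200 mg | 3/6 |
| 100 mg QD | 100 mg | 0/6 |
| 200 mg QD | 200 mg | 1/6 |
| All active | | 6/24 = 25% |
| Placebo | | 0/8 |

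- The total of 5 Grade 3 + 1 Grade 4 = 6, and 6/24 = 25%, matches the protocol's own percentage and the 6 subjects in section 1.4.
- Exact (Clopper-Pearson) 95% intervals: active 9.8% to 46.7%; placebo upper limit 1 − 0.025^(1/8) = 36.9%.
- Fisher, two-sided: with k of the 6 events on placebo, the probability is C(8,k) × C(24,6−k) / C(32,6). The outcomes no more likely than the observed k = 0 are k = 0, 3, 4, 5 and 6: (134,596 + 113,344 + 19,320 + 1,344 + 28) / 906,192 = 0.296.
- Once-daily dosing, as used here, should not be pooled into one rate: the single event was at 200 mg, ten times the top dose of 20 mg. At 100 mg QD there were none in 6 (upper limit 1 − 0.025^(1/6) = 46%).
- The lowest daily dose with an event is 2 × 50 = 100 mg, and 100/20 = 5 times the top dose here.

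**Single-dose evidence** (1.2.5.1 and 1.2.5.3).

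- Study 0976-101: 7 active groups (six fasted, one fed) × 6 = 42, every adverse event Grade 1.
- Study 0976-103: 29 on active drug, highest grade 2.
- Together 0 of 42 + 29 = 71 with Grade 3 or higher; upper limit 1 − 0.025^(1/71) = 5.1%.
- These are adverse-event grades; laboratory grades are not reported. The count takes the fed group as separate people; with the fasted groups alone it is 0/65, upper limit 5.5%.

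**Time to the next scheduled value.** Week 1 is nominally Day 8 (SAP Table 3-1), ± 3 days, so Day 5 to Day 11. Laboratory turnaround is not given, so the number of doses taken before the Day 1 result is read is unknown.

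**Missing Day 1 sample.** Under Protocol 8.3, with no Screening value, baseline becomes Grade 0. Under Protocol 8.6.3 and SAP 7.2.2.1, any later Grade 1 value then counts as treatment-emergent; SAP Appendix 4 starts Grade 1 at 150 mg/dL. A Screening profile would supply the substitute that 8.3 intends.

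**The case against.** The case for leaving the plan alone is substantial.

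- The sponsor saw the risk: section 1.4 names it and gives the lower doses and close laboratory monitoring as the mitigation. The earlier events were asymptomatic and no SAE was reported. Both single-dose studies, one including 20 mg, found no laboratory trend the protocol regards as clinically important.
- A severe Day 1 value is still captured. Lipids are measured again at Weeks 1, 4, 8, 12 and Follow-Up, clinically significant Grade 3-4 laboratory events are to be retested (7.5), and treatment can be stopped for toxicity (6.6).
- History and medications are reviewed at Screening, so known hypertriglyceridemia should surface.
- The documents give no baseline triglycerides for the six affected subjects, so they do not show that a high starting value predicts a severe rise.
- A Screening value would inform only an investigator's opinion, and the Medical Monitor may approve entry despite laboratory abnormalities (4.3).

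All of this stands, and it limits the point to a minor one. It does not remove the gap. The dose reduction and later monitoring do not supply a value before the first dose, and the numeric withholding rules in 7.5 concern liver tests only.

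**Conclusion.** The point holds as a minor, inexpensive improvement for patient safety. The schedule facts are not in doubt: no Screening lipids, a first value drawn at the visit of randomization and first dose, and no required review. The signal behind it is small and uncertain, and it comes from higher doses and mostly twice-daily dosing.

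A reader might infer three stronger things, none of which the documents support:

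- **That some subjects will probably start active drug with unrecognised severe triglycerides.** The documents give no prevalence. Any probability built on an assumed one would count recognised cases too, and would not be a probability of harm.
- **That a quarter of treated subjects may develop Grade 3-4 values here.** The 25% comes from 100 to 200 mg/day, with p = 0.30 against 8 placebo subjects. The rate at 5 to 20 mg is unknown.
- **That the safety analysis is compromised.** The Day 1 sample is taken before dosing, so a proper baseline exists unless that sample is lost.

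**What to change.** Add the lipid profile to the Screening assessments in the synopsis, Protocol 6.2.1, Protocol Appendix 2 and SAP Appendix 1. In 6.3, state that Screening triglycerides are reviewed before randomization. No threshold is needed; exclusion 19 remains the investigator's judgment but has a value to act on, and the substitution rule in 8.3 then works for lipids.

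No extra visit or preparation is needed, because subjects are already told to fast "on the evening prior to the Screening visit to ensure an approximate 8-hour fast prior to the fasted blood sample collection", and the 6-week Screening period leaves time for the result. The cost is one panel per screened subject. The number screened is not given; assuming 30% to 60% screen failure for 125 randomized, it is 125/0.7 = 179 to 125/0.4 = 313 panels. The other downside is possibly a few more screen failures under exclusion 19.
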